### Appendix B

#### **Simulated Patient Cases**

#### **Simulated Patient Case V1**

Field	Value
Username	Test
Password	Test
New ID	0001
First Name	Jane
Last Name	Doe
[contact]
Date of birth	April 15 th 2017

Gender	Female
Weight	7.3 kg
Mid-upper arm circumference	Not Done
Pulse oximetry	Measure Pulse Ox on yourself, plug it in and put
	on the pulse oximeter.
Respiratory rate	Measure RRate on yourself, tap each time you
	breathe.
Temperature	37.8 degrees Celsius
Urgent referral?	No
HIV Status	Negative
Duration of illness/sign/symptom	2 days
Time since last hospitalization	Never
Symptoms	The mother reports Jane is coughing and
	vomiting. Yes, there are tears when crying and
	yes, Jane is able to eat and drink. No other
	symptoms.
Signs	Jane is alert and there are no other signs.

#### **Simulated Patient Case V2**

Field	Value	
Username	Test	
Password	Test	
New ID	4321	
First Name	John	
Last Name	Doe	
[contact]	
Age	Approximately 1 month	
Gender	Male	
Weight	4.2 kg	
Mid-upper arm circumference	134 mm	
Pulse oximetry	Measure Pulse Ox on yourself, plug it in and put	
	on the pulse oximeter.	
Respiratory rate	Measure RRate on yourself, tap each time you	
	breathe.	
Temperature	Not done	
Urgent referral?	Yes	
HIV Status	Positive, but no signs or symptoms from HIV	
Duration of illness/sign/symptom	1 day	
Time since last hospitalization	3 weeks	
Exclusive breastfeeding?	Yes	
Symptoms The mother reports John is wheezing a		
	tears when crying. He is not able to eat or drink	
	anything. No other symptoms.	
Signs	John is not alert but responds to voice. You also	
	notice chest-indrawing but no other signs.	

#### **Simulated Patient Case V3**

Field	Value		
Username	Test		
Password	Test		
New ID	0003		
First Name	James		
Last Name	Doe		
[contact]		
Date of Birth	Approximately 2.5 years		
Gender	Male		
Weight	13.3 kg		
Mid-upper arm circumference	120 mm		
Pulse oximetry	Measure Pulse Ox on yourself, plug it in and put		
	on the pulse oximeter.		
Respiratory rate	Measure RRate on yourself, tap each time you		
	breathe.		
Temperature	38.2 degrees Celsius		
Urgent referral?	No		
HIV Status	Negative		
Duration of illness/sign/symptom	5 days		
Time since last hospitalization	7 months		
Symptoms	The father reports James is coughing and irritable.		
	He vomited his dinner last night and has a runny		
	stool since last night.		
Signs	James is alert and there are no other signs.		

### Appendix C

#### **Think Aloud Script and Triage Tool Instructions**

"You are requested to assess several children who have arrived in the outpatient department. As you go through each patient's simulated patient file using the documentation provided, I ask that you think aloud. This means you say whatever you are thinking, doing, and feeling, as you use the triage tool. Please specifically comment on the layout of the triage tool, icons, and variables requested. Consider if the questions are worded in a way that is easy to understand and whether the order of tasks is appropriate. Feel free to comment on any areas of the tool that you feel could be improved. Let's do a short example. Please think aloud while determining the 4th letter after the letter 'L' in the alphabet.

We will now start the training session. Please verbalize all the thoughts you have about the use of the device and interface. Please provide specific comments on the suggestions and advice provided by the monitor."

[Participant may begin following instructions starting with step 1]

[Once participant has completed the 17 steps of the instructions]

"The training is now over. Do you have any remaining questions or comments about the function or design of the triage app? [Time for remaining questions] The training for testing the mHealth tool is now concluded. Thank you."

#### **Triage Tool Instructions**

- 1. Open the triage tool on the tablet
- 2. Login (provided on data sheet)
- 3. Enter patient ID for new patient (provided on data sheet)
- 4. Enter clinical data (provided on data sheet)
- 5. Record patient results/risk score onto data sheet
- 6. Complete patient record
- 7. Send patient record to dashboard
- 8. Open dashboard
- 9. Identify the highest priority patient (If the participant does not identify the highest priority patient, prompt "can you elaborate on why you chose the selected patient". If the participant identifies this correctly, prompt "please list the reasons why you think this patient is highest priority.")
- 10. Review the three priority identifiers. Prompt "do you think this element is a good indicator of increased risk, and if not, how would you do it differently?"
  - i. Patient is at the top of the list
  - ii. Patient's 'risk' icon is red
  - iii. Patient timer is highlighted
- 11. Prompt ""We will now ask that you observe the dashboard as updates are made to it. Anytime you see a change on the dashboard, indicate to us that you've noticed a change."

The moderator will trigger 3 updates. When the participant identifies and a change, the moderator will ask the following questions:

- a) Describe what you have just seen and what it could mean.
- b) What do you think that triggered that change?
- c) Now that this change has occurred, what do you think the next steps are?
- d) Do you have any questions about this?
- 12. Assign priority patient to consultation room (provided on priority patient data sheet)
- 13. Open digital patient file and compare to data sheet for errors
- 14. Edit patient's 'current status' (provided on priority patient data sheet)
- 15. Close patient file (if indicated on priority patient data sheet)
- 16. From menu, open patient log for last 24 hours
- 17. Log out and shutdown the triage tool

### Appendix D

Triage Tool Tr	aining Questionnaire		
Participant ID:	Date:Time:		
Impact Question #1:	Do you think the triage tool would be a positive addition to the patient risk assessment process at triage?		
Response:			
Question #2:	Do you think the triage tool would improve the patient risk assessment processes at		
Response:	your nospital?		
Question #3:	Do you think the triage tool would be an important part of meeting your information needs related to patient risk levels?		
Response:			
Perceived Usef Question #4:	'ulness Do you think using the triage tool makes it easier for you to identify patients who may		
Response:	be at higher risk and need more attention?		
Ouestion #5:	Do you think the triage tool enables you to identify higher risk patients more quickly?		

#### **Response:**

Question #6:	Do you think using the triage tool makes it more likely that you will identify patients who are higher risk at triage?
Response:	
Question #7:	Do you think that using the triage tool is useful for identifying high risk patients at triage?
Response:	
Question #8:	Do you think the triage tool presents a more equitable process for patient risk assessment at triage?
Response:	
Question #9: Response:	Are you satisfied with the triage tool for risk management of patients at triage?
Question #10:	Do you think you will be able to manage patients risk assessment at triage in a timel manner because of the triage tool?
Response:	

Question	Do you think using the triage tool increases your ability to assess patients' risk levels
#11:	at triage?

#### **Response:**

Question #12:	Are you able to assess patient risk at triage whenever you use the triage tool?
Response:	

#### Perceived Ease of Use

**Question** Are you comfortable with your ability to use the new triage tool? **#13:** 

#### **Response:**

Question	Was learning to operate the triage tool easy for you?	
#14:	was rearring to operate the triage tool easy for you.	
Response:		
Question #15:	Was it easy for you to become skillful at using the triage tool?	
Response:		

Do you find the triage tool easy to use?

#### Question

#16:

#### **Response:**

Question #17:	Can you always remember how to log on to and use the triage tool?
Response:	
User Control Question #18:	Do you find the triage tool gives error messages that clearly tell you how to fix problems?
Response:	
Question #19:	When you make a mistake using the triage tool, do you find you can recover easily and quickly?
Response:	
Question #20:	Do you think the information (such as on-screen messages and other documentation) provided with the triage tool is clear?
Response:	

#### **Healthcare Worker Satisfaction**

QuestionDo you feel like you are well trained and prepped to use the triage tool and standard#21:protocols when they are implemented in the hospital?

#### **Response:**

 Question
 Overall, do you think the triage tool will be a positive addition to your hospital?

 #22:
 Response:

#### **Additional Comments**

Do you have any other feedback for us about the digital triage system?

### Your input and comments are an important part of evaluating the tools and training of this program. Thank you!

### Appendix E

#### **Interview Guide**

Administrative information – Filled out by participant			
ID number:			
Date of informed consent form signed:  D D  -  M M	M - Y Y Y Y		
First Name,	Sex: Female Male Prefer not to say		
Last name,	Age group: <20, 20-30, 30-40, 40-50, 50+		
Program and year graduated			
Total months/years worked in current field			
Total months/years worked at current hospital			
Current department			
Current position			
Administrative information – Filled out by researcher			
Interview Group number (if applicable)			
Does the participant agree to be audio recorded?       Yes       No         (If no, participant will be excluded from the study)       Name of interviewer:       No			
Location of interview:			
Jinia Regional Referral Hospital			
Other:			
Interview start time:       :			
Instructions for gualitative research staff:			

 
Use this document as a guide to conduct the interviews with the hospital staff (HS).
 
Conduct the interview in the language with which the HS feels most comfortable.
 
The interview should take place in a quiet place that allows privacy.
 
Please introduce each question separately. The interview should flow as a conversation. If you notice that the HS is hesitant in answering, does not give an in-depth response, or the response is not satisfactory, please probe or ask follow-up questions, but do NOT prompt any specific answer. Several probes are suggested, and you may also ask follow-up questions that are not listed in this guide but are necessary for the complete expression of the HS's views.
 
Please record the interview using the designated audio recorder and state the HS ID number at the beginning and end of the recording.
 
			

 
All comments from the HS should be recorded.
 
All responses must be kept confidential. Do not discuss or share responses with anyone outside of the PRST study
 
			

team.

#### SCRIPT FOR PROSPECTIVE INTERVIEW

#### *Ex. introduction:*

"Welcome, my name is <interviewer>. I would like to thank you for participating in this interview today. I'm here today to ask you questions and hear your thoughts, opinions, and feelings about the digital triage tool that has been <piloted/operational> at your facility for the past <1 week/6 months>. <Interviewer will provide a brief description of the tool and events to clarify the subject of the interview>. I'll begin by asking you a few questions about yourself and your role at this hospital..."

#### A. Demographic Information

- 1. First, we will start with some questions about yourself;
- 2. What is your first and last name?
- 3. How many years of education and training have you completed?
- 4. What is your highest level of education completed?

#### B. Current role at this facility

- 1. How long have you been employed at this healthcare facility?
- 2. What is your current job title or current role at this facility?
- 3. How long have you been in this role at this facility and how long have you worked here in total?
- 4. What are your responsibilities in this role? *Probes: What does a typical day look like to you?*
- 5. Are you involved in patient care? If yes, explain your patient care responsibilities. (if no, skip question)

Probes: Are you involved with identifying/treating emergency patients? How?

6. Do you have experience with technology? *Probes: At home? At work? At school? Elsewhere?* 

#### C. Digital Triage Tool

#### Usability

- 1. Are you familiar with the PRST Digital Triage Tool?
- In your own words, can you explain what the tool is and what it does?
   Probes: Can you tell me more about risk prediction/triage/patient tracking/etc.
- 3. Are you expected to use the digital triage tool as part of your regular clinical care in the hospital? *Probes: Have you ever used a system like this before? Tell me a bit about it.*
- 4. How do you feel about using a system like this at this facility? *Probes: benefits/challenges?*

#### Training

5. Tell me about the training you received to prepare you for using the digital triage tool. *Probes: who provided the training [PHASE III]-did you attend a training session/ were trained by* 

other hospital staff, who?

- 6. Do you feel you were properly trained to use this tool? Were others? *Probes: Was training long enough? What do think the appropriate length of time and method of delivery of training?*
- 7. Which aspects of using this tool do you think were easy to learn? Which aspects were difficult? *Probes: What barriers did you anticipate/experience during the test period (pilot)?*
- 8. [Newborn] How do you think using this tool will/has affect providing care to newborns at this facility? Probes: How would it be different using the tool with newborns compared with older children?

riobes. How would it be different using the tool with newborns compared with older enharen.

9. What kinds of questions <do you think/have> caregivers or other hospital staff <would have/had> about this tool?

*Probes: basic functioning 'what does it do?'/changes in care/risk prediction/patient tracking?* 

- 10. Are there situations where you think this tool should not be used? If so, what are they? *Probes: The baby is too sick? The hospital is too busy? Understaffed?*
- 11. Are there any changes you would make to this tool before it becomes part of standard clinical care here? If so, what are they?

#### Acceptability

- 12. What do you like (if anything) about this tool overall? What do you dislike (if anything)? *Probe: <key issues that we want responses about. Does it take too long? ... >*
- 13. How do you think other healthcare providers in your hospital <will feel/feel> about this tool? *Probe: Do you think doctors will have a different opinion from nurses?*

#### Parent/Caregiver perspectives

- 14. How do you think mothers and primary caregivers <will feel/feel> about this new tool? *Probes: additional questions/technology/tracking/*
- 15. Do you think fathers/mothers-in-law/other family members, <will feel/feel> the same way? *Probes: Why/Why not?*
- 16. Do you think we should ask caregivers and their families directly?

#### Facility

17. How do you think healthcare administrators and decision-makers in your facility <would/have> react to this tool?

*Probes: Discuss at each level (local, district, national) sequentially. What stakeholders might influence the uptake of this technology?* 

18. What do you think about using Bluetooth technology to track patient movement? Probe: Do you have specific concerns about Bluetooth technology? Have you heard others express concerns about Bluetooth technology? Do you use Bluetooth technology in your personal life? Description of the technology "Bluetooth is a wireless technology standard used for exchanging data between fixed and mobile devices over short distances using short-wavelength UHF radio waves" **Trustworthiness** 

- 19. Would you consider information collected and displayed by this tool trustworthy? Why or why not?
- 20. What information does the tool currently provide that is of interest and of use to you? Probes: Missing Information-Is there information isn't not giving you that you want? Usefulness-Is there information it currently gives that is not useful?

#### Feasibility

21. Do you think this tool is suitable for your facility?

*Probes: For example, staffing availability and skill to use the tool, training, complexity of the tool,* availability of equipment and infrastructure needed for its use, durability and maintenance of tool and components, access to spare parts, protocols and guidelines for use, counselling caregivers and informational materials? What could be benefits/drawbacks?

22. What would need to happen in order to integrate this tool successfully at this facility? Please explain.

Probes: For example, ease of use during a patient visit, integration into current flow of hospital operations, acceptance by administrators, etc.?

- 23. Do you think this tool is suitable for you and the work you do? Why/why not?
- 24. Do you have any other comments about this tool that we did not talk about?

## Abstract

Background: Sepsis is the leading cause of death and disability in children. Every hour of delay in treatment is associated with an escalating risk of morbidity and mortality. The burden of sepsis is greatest in low- and middleincome countries where timely treatment may not occur due to delays in diagnosis and prioritization of critically ill children. To circumvent these challenges, we propose the development and clinical evaluation of a digital triage tool that will identify high risk children and reduce time to treatment. We will also implement and clinically validate a Radio-Frequency Identification system to automate tracking of patients. The mobile platform (mobile device and dashboard) and automated patient tracking system will create a low cost, highly scalable solution for critically ill children, including those with sepsis.

Methods: This is pre-post intervention study consisting of three phases. Phase I will be a baseline period where data is collected on key predictors and outcomes before implementation of the digital triage tool. In Phase I, there will be no changes to healthcare delivery processes in place at the study hospitals. Phase II will involve model derivation, technology development, and usability testing. Phase III will be the intervention period where data is collected on key predictors and outcomes after implementation of the digital triage tool. The primary outcome, time to treatment initiation, will be compared to assess effectiveness of the digital health intervention.

Discussion: Smart technology has the potential to overcome the barrier of limited clinical expertise in the identification of the child at risk. This mobile health platform, with sensors and data-driven applications, will provide real-time individualized risk prediction to rapidly triage patients and facilitate timely access to life-saving treatments for children in low- and middleincome countries, where specialists are not regularly available and deaths from sepsis are common.

Trial registration: Clinical Trials.gov Identifier: NCT04304235, Registered 11 March 2020.

Keywords: Sepsis, Triage, Digital triage tool, Resource limited settings

BMC

Department of Anesthesiology, Pharmacology & Therapeutics, University of British Columbia, [name], Canada

Full list of author information is available at the end of the article

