### 11. Outcomes

### **Primary Outcomes**

- 1. **Model Development:** Hospital admission (within 5 days of assessment) status determined from hospital records and information system, and a follow up call 7 days post discharge (to ascertain outcome). This will inform development of a clinical prediction model based on need for hospital admission.
- 2. Effectiveness Evaluation of Digital Triage Tool: Time to administration of an appropriate sepsis bundle of care, which includes at least one of antibiotics, intravenous

fluids, or oxygen as appropriate for age and clinical syndrome (treatment determined and administered by **hospital staff**). This will allow us to quantify the change from baseline in the proportion of children in each triage category (emergency, priority, queue) receiving treatment within 60 minutes of arrival at hospital.

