#### **Outcomes Analysis**

We will compare the proportion of children at the two intervention sites receiving a completed bundle within 60 minutes to the historical and the contemporaneous control group (Marascuillo procedure). The median time to an appropriate bundle of care will be compared using a Mann–Whitney U test. The triage prioritization between the phases and the proportion of children who received and appropriate bundle of care within each triage categorization will be compared with Fisher's exact tests. Segmented regression analysis of the interrupted time series of the pre- and post- intervention periods will be used to assess immediate effects and effects over time, controlling for prior trends that may continue without our intervention. Quantile regression will be used to estimate the median differences. We will compare the estimated times at end of the intervention period with the expected counterfactual value, had the pre-intervention trend continued as if the intervention never occurred. We will compare the time to event (treatment bundle) using the Kaplan-Meier estimator with censure at 180 minutes. Secondary outcomes will be compared using generalized estimating equations.

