#### **Economic Evaluation**

We will conduct a cost-effectiveness analysis of Smart Triage by calculating the cost per averted year of life lost (YLL) using decision analysis. Previous models (21) and expert opinion has been consulted for potential pathways of healthcare utilization. We will model uncertainty using probabilistic sensitivity analysis and will take a societal perspective as our base case.

Probabilities of healthcare utilization will be calculated via primary data from the Smart Triage case report form. The primary outcome of "time to bundle of care" will be linked to mortality via existing evidence (22) as required in order to calculate YLL, as Smart Triage was not originally powered to detect mortality. We will use the World Health Organization's life expectancy data in Uganda (23) to calculate projected YLL before and after program implementation. Costs of healthcare utilization is available through existing literature (21, 24), and indirect costs due to lost wages will be gathered as primary data in Smart Triage. Costs of program setup and maintenance will be tracked from study expenses and incorporated into the analysis.

To contextualize our results for informing budgetary decisions of scaling-up Smart Triage, we will estimate a projected budget impact of scale up given the disease burden of pediatric sepsis in Uganda (25), as recommended for newly proposed healthcare programs (26). The results of this preliminary budget impact analysis can be refined in further multicenter trials and can be compared to that of other programs to facilitate healthcare resource allocation in Uganda.

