### Outcomes

#### Primary outcomes

**For model development** Hospital admission (within 5 days of assessment) status determined from hospital records, and a follow up call 7 days post discharge. This will inform development of a clinical prediction model based on need for hospital admission.

For effectiveness evaluation of digital triage tool An increase of at least 20% in the proportion of critically ill children (emergency and priority cases) receiving an appropriate bundle of care within 60 min of arrival at the hospital. An appropriate bundle of care is defined as at

least one of antibiotics, intravenous fluids, or oxygen as appropriate for age and clinical syndrome as determined and administered by **hospital staff**.

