#### **Outcomes** analysis

We will be conducting our primary analysis using a difference in differences method. For our primary analysis, a logistic regression model for receipt of bundle of care within 1 h will be fit including: 1) phase of study (pre vs. post PRST) and 2) group (intervention versus control) as independent dummy variables and 3) their interaction. The interaction term corresponds to the difference in log-odds between groups in baseline vs intervention and it's exponent as the ratio of odds ratios. We will summarise this difference by estimating the marginal effect (risk difference) of phase in both the control and intervention groups. The difference of these marginal effects is the so-called 'difference in difference' for a binary outcome [24]. Confidence intervals will be based on the delta-method, or bootstrapping, where appropriate. A similar approach will be used for binary secondary outcomes (mortality, readmission), or quantile regression for median time to bundle of care, a non-parametric outcome.

Subgroup analyses specified a priori include Ugandan vs. Kenyan intervention site, young infant (under 2 months old) vs. children under 5 vs. older children, and presentation during day-shift hours versus night-shift hours (if applicable). We will also perform subgroup analyses on each triage category (emergency, priority, queue); patients from the pre-intervention phase will be retroactively categorized into these subgroups for this analysis. These subgroup analyses will be conducted with the inclusion of a three-way interaction between said variable, phase, and group. Statistical significance will be based on a likelihood ratio test comparing models with and without this term. This three-way interaction term would represent potential interactions between different subgroups and our difference in odds ratio obtained in our primary analysis, and results will again be presented on the risk difference scale based on marginal effects. This method of subgroup analysis sometimes termed a difference in difference in differences method.

Although none are expected, if there are any time varying confounders identified during the study that differ between intervention and control (health system or policy changes, natural events, changes in patient populations etc.) they will be included in above models as sensitivity analyses.

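### The primary effectiveness endpoint differs between sections, and section 17 of protocol v5.0 compares it in several ways without naming a primary contrast, so no single result decides effectiveness

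*Combined protocol and SAP*

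**What the plan says.** The file holds two protocols: the published one (June 2020) and version 5.0 (October 2020).

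**Time as primary.** The published abstract states: "The primary outcome, time to treatment initiation, will be compared to assess effectiveness of the digital health intervention". In v5.0 section 17, Economic Evaluation, time to bundle is called the primary outcome and "will be linked to mortality via existing evidence".

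**Time, summarised as proportions.** v5.0 section 11 names "Time to administration of an appropriate sepsis bundle of care" and continues: "This will allow us to quantify the change from baseline in the proportion of children in each triage category", meaning treatment within 60 minutes of arrival.

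**Proportion as primary.** The published Primary outcomes section has "An increase of at least 20% in the proportion of critically ill children", restricted to emergency and priority cases and a 60-minute limit. For the primary analysis in the published Outcomes analysis section, "a logistic regression model for receipt of bundle of care within 1 h will be fit", with phase, group and their interaction; quantile regression for median time appears beside the secondary outcomes. Both sample-size sections use the proportion treated within one hour, without a triage restriction.

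**Analyses.** v5.0 section 17, Outcomes Analysis, does not contain the difference-in-differences model. It lists the Marascuillo procedure on the 60-minute proportion, a Mann–Whitney test on time, Fisher's exact tests on triage prioritisation and within triage categories, segmented regression (immediate effect, effect over time, end-of-period counterfactual) and quantile regression. It adds: "We will compare the time to event (treatment bundle) using the Kaplan-Meier estimator with censure at 180 minutes". None is labelled primary. The published protocol applies an alpha of 0.05 to every outcome analysis.

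**The concern.** A study needs one result that settles whether the tool worked. Here the outcome variable, its population and the analysis all change with the section consulted. The version dated later drops the only analysis that was designated primary.

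Two consequences follow. First, if any of several contrasts at 0.05 could support a claim of effectiveness, the error rate of the overall claim exceeds 0.05. Second, the 60-minute proportion and the time distribution can give opposite answers, and no rule says which prevails.

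**Working it through.** **1. What the study is sized on.** v5.0 section 13 and the published sample-size section both start from 27% treated within one hour, with alpha 0.05 and 80% power, and state 750 per group. For the published 20% relative increase the target is 0.27 × 1.20 = 0.324. The pooled two-proportion formula, with mean proportion 0.297, gives

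n = [1.96·√(2 × 0.297 × 0.703) + 0.842·√(0.27 × 0.73 + 0.324 × 0.676)]² / 0.054² ≈ 1,123 per group.

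The 750 does not reproduce; power at 750 is 62.9%. That is a separate matter. What counts here is that the inputs are proportions, so the study is sized on the 60-minute proportion and not on time. The documents state no error rate for the set of analyses, so there is no such figure to reproduce.

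**2. Why the endpoints differ.** If 27% are treated by 60 minutes, then 0.27 < 0.50 and the median exceeds 60 minutes. The same holds at the target, since 0.324 < 0.50. With log-normal waits and a log-scale SD of 1 (assumed), the median is 60 × exp(0.613) ≈ 111 minutes. The proportion describes the lower tail; the median describes waits well beyond it.

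**3. Error rate if tests were independent.** The chance of at least one significant result is 1 − 0.95^k: 9.8% for k = 2, 18.5% for k = 4, 30.2% for k = 7 and 40.1% for k = 10. This overstates the case, because the contrasts reuse the same children.

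**4. Error rate allowing for dependence.** This used 4,000 simulated null trials with 750 children per group and three groups (pre, post, contemporaneous control). Waits were log-normal with 27% under 60 minutes. Assumptions not in the documents: the wait distribution, a 10/30/60% triage mix, a log-rank test for the Kaplan–Meier comparison, and no clustering by site. Correlations among the pre/post proportion, Mann–Whitney, median and log-rank statistics were 0.59 to 0.94.

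| Contrasts counted as evidence | Any significant | Favourable only |
|---|---|---|
| Pre/post proportion, Mann–Whitney | 8.0% | 3.5% |
| Those two, quantile, log-rank | 11.1% | 5.1% |
| Marascuillo, Mann–Whitney, segmented level and slope, quantile, log-rank | 18.1% | 8.5% |
| Same, with the two proportion comparisons unadjusted | 22.4% | 10.8% |
| Marascuillo set plus three category Fisher tests | 27.1% | 13.4% |
| Unadjusted set plus three category Fisher tests | 30.1% | 15.0% |

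The 95% simulation error is about ±0.8 points at 8% and ±1.4 points at 30%. One two-sided test at 0.05 has 5% and 2.5% in the two columns.

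**5. Can the endpoints disagree?** Two constructed shifts were simulated at 750 per group; ranges are across repeated simulations.

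- 5.4 points of children (32.4 − 27.0) move from 60–90 minutes to under 60: the proportion test is significant in 62–64% of trials, in line with the 62.9% from step 1, and Mann–Whitney in 5–9%.
- Waits beyond 90 minutes shorten by 20%: the proportion test is significant in 4–6%, and Mann–Whitney in 69–72%.

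**The case against.** The strongest reply is that the published protocol does name a primary analysis: one endpoint, one model, one interaction term. That is correct, and a reader should not infer that no primary was ever designated. But v5.0 is later and its section 17 leaves that model out, so the two documents give different analyses with no statement of which governs.

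Second, v5.0 section 11 can be read as a measured variable (time) with its summary (the 60-minute proportion), not two rival endpoints. That is fair for section 11. It does not cover the published abstract, nor the change of population between each triage category, emergency plus priority, and all children.

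Third, a reader might infer a false claim of effectiveness about 30% of the time. The documents do not support that. The figure counts significant results in either direction, including ones where the tool looks worse, and it needs about ten contrasts, a list the documents never give. Section 17 uses quantile regression to estimate, names no test with Kaplan–Meier, and draws the segmented-regression effects from one model. The Marascuillo procedure already controls its own pairwise comparisons. The prioritisation test concerns triage mix, not timeliness, and is excluded above. The rule of 0.05 for all outcome analyses is in the published protocol; applying it to each v5.0 comparison is an inference.

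Fourth, the shifts in step 5 were built to separate the endpoints, and the statistics are otherwise well correlated. They show that disagreement is possible, not that it is likely.

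**Conclusion.** The concern holds in this form. The primary effectiveness endpoint is inconsistent in variable and population, and v5.0 section 17 lists several effectiveness comparisons with no primary, order or multiplicity rule, while omitting the published primary model. Nothing says the investigators would choose a result after the fact; the plan simply does not prevent it.

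The chance of at least one significant result under a true null is roughly 8–30%. In the favourable direction it is roughly 4–15% against 2.5%, or 1.4 to 6 times nominal (3.5/2.5 and 15.0/2.5). The spread reflects which contrasts count as evidence of effectiveness, which the plan leaves open, and the values rest on the assumptions in step 4. Two conclusions need no simulation: the sections conflict, and at 27% within 60 minutes the median lies beyond the cut-off, so the two endpoints measure different parts of the distribution.

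**What to change.** - **Endpoint.** In v5.0 sections 11 and 17 (Outcomes Analysis), and in the published abstract, Primary outcomes and Outcomes analysis text, name the proportion receiving the bundle within 60 minutes of arrival as the single primary effectiveness endpoint.
- **Population.** State one, reconciling the restriction to emergency and priority cases with the unrestricted sample-size sections. If the restriction stays, the baseline rate and sample size must be restated for that group: under the assumed 10/30/60% mix, 750 children would include only 0.40 × 750 = 300 such cases.
- **Contrast.** Name one, tested at two-sided 0.05, reconciling section 17 with the published difference-in-differences interaction.
- **Other analyses.** Make time to bundle the key secondary, tested only if the primary is significant. Report the remaining section 17 analyses as supportive estimates with 95% confidence intervals and no significance claims.
- **Economic Evaluation.** Keep time to bundle as the model input linked to mortality, but do not call it the primary outcome.

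No new data are needed; the cost is an amendment to the outcome and analysis text, plus a recalculated sample size if the population is restricted. The price is that a positive result on time alone could no longer be claimed as the primary result.
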